In this proposed pilot study, the safety of delayed rewarming will be assessed in infants under the age of 12 months who require cardiopulmonary bypass surgery for repair of congenital heart defects. **It is proposed that the delayed rewarming technique will be safe and that a trend toward lower serum biomarker levels will be seen in the experimental group compared to the standard of care group.** Successful completion of this pilot safety study will lay the foundation for a future adequately powered efficacy study to determine if the delayed rewarming technique leads to improved developmental outcomes.

Specific Aim 1: Evaluate safety of delayed rewarming in infants following congenital heart disease surgery through intensive care unit level monitoring of parameters including hemodynamic status, coagulopathy, infection, hyperthermia and subcutaneous fat necrosis. In this pilot study, infants under the age of 12 months with congenital heart disease requiring surgical palliation with cardiopulmonary bypass will be randomly assigned to the standard of care versus experimental group. The experimental treatment is “delayed rewarming” and will be defined as the cessation of rewarming on cardiopulmonary bypass at 35°C. There will be 12 hours of controlled rewarming to 36.5°C via the use of a programmable body temperature regulating blanket that is FDA approved for this use. Safety will be determined by continuous close monitoring in the post-operative setting in the Pediatric Intensive Care Unit for adverse effects on hemodynamic status (bradycardia, junctional ectopic tachycardia, hypotension and need for additional medication to support heart rate or blood pressure), for coagulopathy (lab evidence of disseminated intravascular coagulation, chest tube output and need for transfusion of blood products), infection (such as pneumonia), effects on other end organs (monitored via lab testing for kidney function daily), frequency of infants with **hyperthermia** and lastly close inspection of the skin to insure there is no evidence for subcutaneous fat necrosis. My hypothesis is that the “delayed rewarming” group will not demonstrate a higher frequency or severity of adverse events compared to the standard of care group.

Specific Aim 2: Compare early and late biomarkers for adverse developmental outcomes between standard of care and “delayed rewarming” groups including serum biomarkers of brain injury, electroencephalogram (EEG) and developmental outcomes.

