Figure 3b: Research design for KL2 project

Randomization: We will randomize in a one to one fashion. A random number generator will be used with those numbers being translated into a list of sequentially numbered opaque envelopes that will be opened by the principal investigator (PI) in order at the time of randomization following the informed consent process.

Recruitment: [name] and [name] are pediatric cardiologists and follow expectant mothers weekly or biweekly throughout a pregnancy known to be complicated by a diagnosis of congenital

heart disease. [name] and [name] will refer appropriate patients to [name] (PI) for consideration of enrollment. The PI will meet with the pregnant mother and father in the outpatient setting several weeks after the diagnosis has been made, giving the family time to come to terms with this new diagnosis. At the first meeting with the PI, the family will be informed about the research study and given informational handouts. Another meeting will occur prior to the admission during which the congenital heart surgery will be performed. At this second meeting, informed consent documentation will be reviewed and signatures obtained from parents willing to participate. For infants who need congenital heart surgery within the first few days of life or for those in whom a fetal diagnosis was not made, the PI will obtain informed consent from parents in the hospital prior to surgery. The envelopes for randomization will be opened at the time consent is obtained to insure that there is adequate time to arrange for the type of post-operative care the infant will receive (intervention versus standard of care).

Standard of care group: For infants assigned to the standard of care group, the congenital heart surgery will be performed according to usual practice with the degree of intra-operative hypothermia determined by the cardiothoracic surgeon and his team based on the anticipated complexity of the case. Following completion of the surgical procedure, the infant will be rapidly rewarmed on cardiopulmonary bypass at a rate of 1°C each 3-5 minutes. The infant will achieve normothermia of 36-37°C and be transported to the Pediatric Intensive Care Unit (PICU) for routine post-operative monitoring. Standard of care procedure in the post-operative setting is clearly defined below on Figure 4.

Figure 4: Standard of Care Temperature Management after Bypass

LOCATION	PERSON RESPONSIBLE	RECORDING SITE	GOAL TEMP	FACTORS

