In order to carefully define what is considered an adverse event, a retrospective chart review was performed for 15 infants in the past 12 months who survived congenital heart surgery with cardiopulmonary bypass at MMC. Of the 15 infants, the mean age at the time of surgery was 148 days with a range from 4 to 356. Of the 15 infants, 10 were male and 5 female. These infants had a mix of cardiac lesions similar to those who would be enrolled in this study. See Table 1 for a full outline of parameters that will be considered acceptable for infants enrolled in the study, which are based on the retrospective review of 15 survivors. Using these parameters to define what has been previously consistent with “safe”, any infant enrolled in the proposed study with results outside these parameters will then be considered as an adverse event and the data safety monitoring board will be informed. If a severe adverse event occurs in either Phase 1 or Phase 2 of the proposed research protocol, no additional infants will be enrolled and all experimental exposures will be suspended until a decision is made by the DSMB.

Table 1: Definitions of Serious, Moderate and Other Adverse Events

Serious Adverse Events	Reported to DSMB within 24 hours of occurrence
Mortality	Death within 48 hour period following surgery
Need for resuscitation	Need for cardiopulmonary resuscitation within 48 hours of surgery
ECMO after surgery	Persistent need for bypass (ECMO) following surgery; STUDY EXCLUSION CRITERIA
Return to OR on day of surgery	Unexplained hemorrhage prompting return to the OR for exploratory surgery
Stroke or seizures	Ischemic or hemorrhagic stroke OR status epilepticus OR clinical or electrographic seizures
Moderate Adverse Events	Reported to DSMB within 48 hours of occurrence
Bradycardia	Clinically significant heart rate <100 bpm for >30 minutes*
Tachycardia	Clinically significant heart rate > 160 bpm for 30 minutes*
Arrhythmia (JET)	Any occurrence of JET(Junctional ectopic tachycardia) OR other arrhythmia
Hypotension	Systolic BP< 70 mm Hg OR Diastolic BP< 30 mm Hg *
Coagulopathy	INR > 2.2 OR PTT > 74 seconds Thrombocytopenia with platelets < 50,000 Chest tube output more than 5 cc/kg/hr OR 40 cc/kg in an 8 hour shift
Leukopenia	White blood cell count < 4,000
Other adverse Events	Reported to DSMB within 7 days

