Data will be collected at the bedside and through chart review. A study ID number will be assigned to each infant and study documents will all use this ID number to combine data. Identifiable data will be stored separately. Preoperative (baseline) variables including gender, age in months and type of congenital heart lesion will be collected. A baseline s100b and NSE will also be considered pre-operative variables. Intraoperative variables including aortic cross clamp time, cardiopulmonary bypass time, lowest temperature during surgery, time for rewarming on bypass in all 3 groups and s100b and NSE at the completion of cardiopulmonary bypass will be collected. Postoperative variables include temperature, heart rate, blood

pressure, presence or absence of an arrhythmia such as JET, pressor use, frequency of transfusions, hours of intubation, coagulation dysfunction, frequency and type of infection and presence or absence of subcutaneous fat necrosis for 48 hours after surgery. S100b and NSE will be compared at the 4 post-operative time points as well.

Success of randomization will be assessed by comparing baseline characteristics in the two treatment groups; we acknowledge that randomization may not be entirely effective with such a small sample size and we will examine the data for biases to be considered in interpreting our findings. For this safety study, primary outcomes will be composite outcomes and will include the frequency of serious adverse events as well as the frequency of any adverse events (see Table 1) and will be compared among treatment groups using chi square tests or Fisher's exact tests, as appropriate. The frequency of individual adverse events such as hemodynamic compromise, arrhythmia, coagulopathy, infection, hyperthermia and subcutaneous fat necrosis will also be examined. Biomarkers (s100b and NSE) will be examined using a repeated measures analysis of variance, with the time * treatment interaction serving as the hypothesis test.

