Stroke or seizures	Ischemic or hemorrhagic stroke OR status epilepticus OR clinical or electrographic seizures
Moderate Adverse Events	Reported to DSMB within 48 hours of occurrence
Bradycardia	Clinically significant heart rate <100 bpm for >30 minutes*
Tachycardia	Clinically significant heart rate > 160 bpm for 30 minutes*
Arrhythmia (JET)	Any occurrence of JET(Junctional ectopic tachycardia) OR other arrhythmia
Hypotension	Systolic BP< 70 mm Hg OR Diastolic BP< 30 mm Hg *
Coagulopathy	INR > 2.2 OR PTT > 74 seconds Thrombocytopenia with platelets < 50,000 Chest tube output more than 5 cc/kg/hr OR 40 cc/kg in an 8 hour shift
Leukopenia	White blood cell count < 4,000
Other adverse Events	Reported to DSMB within 7 days
Hypertension Pressor Use Days of intubation Infection Subcutaneous fat necrosis	Systolic BP > 100 mmHg OR Diastolic BP > 80 mmHg* Treatment with more than 2 pressors for more than 7 days Intubated for longer than 5 days Occurrence of urinary tract infection, pneumonia OR other wound infection Any occurrence

*resulting in hemodynamic compromise and/or need to administer medications to support heart rate and/or blood pressure

Stopping Rules: DSMB has the responsibility of pausing or stopping the trial in the case of 1) any serious adverse event probably or definitely related to study intervention OR 2) two or more unexpected or unanticipated adverse events of same or similar type

Adequacy of sample: We aim to enroll 30 infants and randomize 15 to the standard of care and 15 to the experimental group. With 15 infants in each group, we have determined that we will not have the necessary power to permit definitive analysis of the results, but will use these preliminary data to establish whether or not the treatment is safe and well-tolerated for the design of future, larger adequately powered trials.

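### Aim 1 hypothesises no higher severity of adverse events, but no planned per-infant analysis separates Moderate from Other events; add a supporting worst-tier comparison beside the two composites

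*Combined protocol and SAP*

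**What the plan says.** - **Hypothesis (Specific Aim 1).** The delayed-rewarming "group will not demonstrate a higher frequency or severity of adverse events compared to the standard of care group". Frequency and severity are both named.
- **Grading (Table 1, "Definitions of Serious, Moderate and Other Adverse Events").** Events fall into three tiers, to be reported to the DSMB within 24 hours, 48 hours and 7 days respectively.
- **Primary analysis (ANALYSIS).** The "primary outcomes will be composite outcomes and will include the frequency of serious adverse events as well as the frequency of any adverse events"; these "will be compared among treatment groups using chi square tests or Fisher's exact tests, as appropriate".
- **Further analysis (same section).** "The frequency of individual adverse events such as hemodynamic compromise, arrhythmia, coagulopathy, infection, hyperthermia and subcutaneous fat necrosis will also be examined".
- **Size (Adequacy of sample).** "We aim to enroll 30 infants and randomize 15 to the standard of care and 15 to the experimental group". The same paragraph says "we will not have the necessary power to permit definitive analysis of the results". The documents give no alpha, event rate, effect size or margin.

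**The concern.** Every planned safety comparison is a frequency. With none as the lowest level, the Table 1 tiers form a four-level scale with three cut points: Other or worse, Moderate or worse, and Serious. The any-event composite uses the first and the serious composite the third. Nothing uses the middle one.

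The middle cut matters because of what lies just above it. Bradycardia, hypotension, arrhythmia and coagulopathy are Moderate, and the protocol's own text on managing complications expects bradycardia to be the most likely one. If many infants in both arms have some Other-tier event, such as prolonged intubation or infection, and delayed rewarming moves some of them into Moderate, both primary composites stay the same. The severity half of the hypothesis would then be reported without an analysis able to show that change.

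**Working it through.** **1. The plan's own figure.** 15 + 15 = 30 agrees with the stated total. There is no power calculation to reproduce.

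**2. Inputs.** From the documents: 15 per arm, 1:1 allocation, three tiers, two composites, chi-square or Fisher. Assumed, because the documents are silent: two-sided 5%, the tier rates, the size of any shift, and that each composite is scored yes/no per infant. Single-composite powers are exact binomial sums. Either-composite and ordinal powers come from simulation (at least 3,000 trials per scenario) using the Wilcoxon-Mann-Whitney test on worst tier. Chi-square is uncorrected.

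**3. A shift from Other to Moderate only.** Tiers are in the order none/Other/Moderate/Serious.

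| | Control 20/60/10/10 | Experimental 20/20/50/10 |
|---|---|---|
| Any event | 1 − 0.20 = 0.80 | 1 − 0.20 = 0.80 |
| Serious | 0.10 | 0.10 |
| Moderate or worse | 0.10 + 0.10 = 0.20 (3 of 15) | 0.50 + 0.10 = 0.60 (9 of 15) |

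Both composites have the same true rate in each arm, so any rejection is a false positive: about 2% for either Fisher composite and about 7% for either unadjusted chi-square composite. The ordinal test rejects 29 to 30% of the time. The probability that an experimental infant fares worse than a control is:
- experimental strictly worse: 0.20 × 0.20 + 0.50 × 0.80 + 0.10 × 0.90 = 0.53
- ties: 0.20 × 0.20 + 0.20 × 0.60 + 0.50 × 0.10 + 0.10 × 0.10 = 0.22
- probability of worse, ties split: 0.53 + 0.22/2 = 0.64

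**4. A proportional shift.** Control 50/20/20/10, common odds ratio (OR) 3, using q = 3p/(1 − p + 3p):
- any event: 1.5/2.0 = 0.75
- Moderate or worse: 0.9/1.6 = 0.56
- Serious: 0.3/1.2 = 0.25

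| Test at OR 3 | Power |
|---|---|
| Fisher, serious | 8.5% |
| Fisher, any | 15.7% |
| Either Fisher composite | 21.8% |
| Chi-square, any | 29.3% |
| Either chi-square composite, unadjusted | 39.2% |
| Ordinal worst tier (exact) | 34.3% |

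Ratios: 34.3/21.8 = 1.6 over either Fisher composite; 34.3/29.3 = 1.2 over the better chi-square composite; 34.3/39.2 = 0.9 over either chi-square composite.

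Across eight assumed control distributions (any event 40 to 90%, serious 5 to 25%) at OR 3:
- Ordinal power is about 27 to 35% with the exact test.
- Over either Fisher composite the gain is about 1.5 to 2.4 fold, the top of the range coming from the large-sample version of the rank test.
- Over the better single chi-square composite it is about 1.0 to 1.6 fold.
- Over either unadjusted chi-square composite it is roughly nil, although that rule rejects about 5 to 10% of the time under no effect. Under no effect the exact ordinal test rejects about 4 to 5% of the time and either Fisher composite 1.4 to 3.6%.

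**5. Harm concentrated at one cut.**
- Serious 10% to 40% (50/20/20/10 to 40/10/10/40): Fisher serious 32 to 33%, ordinal 21 to 23%.
- Any event 50% to 90%, with Moderate 20% to 30% and Serious fixed at 10%: Fisher any 53.6%, ordinal 34.8%.

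**The case against.** A reader might infer that the plan discards the tiers. It does not. The serious composite is itself a severity cut, so two of the three cut points are used. The individual-event frequencies include arrhythmia and coagulopathy, both Moderate, so an excess of those would be visible event by event, and the DSMB judges the clinical significance of each event. What remains is that event-by-event counts do not give a per-infant severity comparison.

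A reader might also infer that an ordinal test doubles power. That holds against a single Fisher composite under a near-proportional shift, and part of it reflects Fisher's conservatism (size about 1.7% for any event when half the controls have one). The plan also allows chi-square, against which the gain is small or absent.

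The scale is imperfect too. The tiers carry reporting deadlines, not a validated severity grade; leukopenia (Moderate) would outrank pneumonia or more than 5 days of intubation (both Other). This stands, and it is a reason to keep the analysis supporting. Finally, the plan already concedes low power. That is true, but it does not explain why half of a stated hypothesis has no analysis that uses the grading the trial already assigns.

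**Conclusion.** The gap follows from the text and needs no simulation: severity is hypothesised, and no per-infant analysis distinguishes Moderate from Other. Under a pure Other-to-Moderate shift the composites cannot respond, because their true rates are equal in the two arms. The 2% against 29 to 30% contrast illustrates this under assumed rates.

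The documents do not support two stronger conclusions: that the ordinal test is generally about twice as powerful, or that it should replace the serious-event composite as primary. The first depends on the tier rates, a proportional shift and the choice of Fisher as comparator. The second would cost power where serious harm rises, which a safety study should least wish to miss.

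Even with the addition, power stays near 50% or less up to OR 4. With no margin set, a non-significant result would not establish the hypothesis of no higher severity. The estimate and its interval are what the addition contributes. It should be made, but it does not undermine the trial.

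**What to change.** In ANALYSIS, keep both composites as primary and add a supporting severity analysis:
- one value per infant, the worst Table 1 tier (none < Other < Moderate < Serious), tabulated by arm;
- either the probability that a delayed-rewarming infant fares worse than a control (Wilcoxon-Mann-Whitney, ties split) or a proportional-odds ratio, chosen in advance, with a 95% interval;
- a sentence saying that worst tier is a proxy for severity and that non-significance will not be read as evidence of no increase.

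State the scoring where Table 1 is unclear:
- ECMO is listed both as a serious event and as a study exclusion, while envelopes are opened at consent, before surgery. Say how an already randomised infant who needs it is counted.
- Hyperthermia is an Aim 1 safety parameter with no Table 1 tier.
- More than 7 days of pressors and more than 5 days of intubation cannot be observed within the 48-hour collection period given in ANALYSIS. Reconcile the two.

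These gaps already affect the any-event composite, so settling them helps the primary analysis as well. The cost is a paragraph of text and a short scoring table, with no extra infants or visits. Collection beyond 48 hours would be needed for the two long-duration items if they are kept on the scale.

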2.1 Compare levels of serum biomarkers of brain injury in the acute post-operative setting including serum s100b and NSE (neuron specific enolase). Levels will be assessed in both groups in the pre-operative setting for baseline and

serially in the post-operative setting for 72 hours. It is hypothesized that infants in the “delayed rewarming” group will show a trend toward lower levels of biomarkers of brain injury.

[figure not shown]
2.2 Record EEG and monitor seizure frequency in infants for 48 hours following CHD surgery. Seizures, if they occur, will be treated in both groups and the duration quantified in seconds. EEG is needed primarily to rule out potential confounding effects of seizures on later developmental outcome. It is hypothesized that there will be infrequent seizures and no differences in seizure frequency or duration between groups.

2.3 Compare developmental outcomes using Bayley Scales of Infant Development (Bayley 3). Bayley testing will be performed on infants at either 6 or 12 months of age depending on the infant’s age at the time of surgery. It is hypothesized that infants in the “delayed rewarming” group will show a trend toward improved Bayley scores compared to the standard of care group.

Preliminary data:

A retrospective review of cases of congenital heart disease requiring surgical palliation was performed for cases from January 2011 to May 2014. The database was provided by [name] to [name] for the purposes of this analysis. This database is kept for quality work in [name] office. Please see the attached letter of support for this project from [name]. In this review, there were 191 surgeries performed on infants under the age of 12 months by [name] in the 41 month interval (average 4.6 surgeries per month). Some infants required multiple surgeries and therefore the total number of surgeries (191) reflects 119 individual infants. The proposed research project includes only infants undergoing cardiopulmonary bypass (CPB) for the first time. In this sample, there were 88 CPB surgeries. Ten infants had surgery requiring CPB on more than one occasion and thus eliminating repeat exposures to cardiopulmonary bypass, 76 of the 88 total surgeries would have met inclusion criteria for enrollment into this research project (1.9 infants per month or 22 per year). Anticipating a 2 year period of recruitment, there should be approximately 44 eligible infants and we will seek to enroll 30.

[figure not shown]

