2. Residual blood that would otherwise be wasted from a clinically obtained sample will be collected and used for testing for biomarkers of neuronal injury (s100b and NSE). These samples will be obtained at the following 5 intervals; the pre-operative setting for baseline, post-operatively after bypass, at post-op hour 24, at post-op hour 48 and at post-op hour 72. [name], Research Program Director of the BioBank and Research Laboratory Services (RLS) at Maine Medical Center Research Institute has kindly agreed to assist with technical support for the processing of the s100b and NSE testing. The s100b testing is a serum ELISA test run on a kit provided by Millipore™. This test requires 100µL of serum per sample to be tested. This ELISA may be run on a sample that has been previously frozen. The NSE test is also run on serum and is an ELISA test requiring 100µL of serum that may also be used on a frozen stored specimen. The company providing the NSE sample kit is R&D Systems. The stored samples will then be run in batches once the full collection period is complete. The collection of the samples and the handling of samples will be facilitated by the PI and [name], research

coordinator participating in the project (please see the attached letter of support from [name], VP Neuroscience Service Line who is funding the research coordinator position).

3. Bayley Infant Scales of Development (Bayley 3) will be performed between age 9 months and 2 years. The testing will be performed by a physical therapist who assesses fine and gross motor indices and by a Master's level psychologist who assess both the cognitive and language development components. Severe developmental disability will be defined as a Bayley Mental Development Index score that is 2 standard deviations below the mean score (eg. below 70)⁵. Moderate developmental disability will be defined as a Bayley Mental Development Index score that is 1 to 2 standard deviations below the mean score (eg. below 70-84)⁵. The parents of research subjects will have the opportunity to meet with a member of the developmental assessment team to review results of the testing.

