Experimental group: For infants assigned to the experimental group, the congenital heart surgery will be performed according to usual practice as detailed in the standard of care group section above, with depth of hypothermia dictated by the complexity of the congenital heart lesion to be repaired. Upon completion of the surgical procedure, partial rewarming will occur on cardiopulmonary bypass, but will stop when the infant reaches 35°C.

The infant will be transported from the operating room to the PICU at 35°C and placed on a servo-controlled blanket with an esophageal temperature probe placed. Through use of the servo-controlled blanket, the rate of rewarming will be carefully regulated with increases in temperature of 0.3°C every 2 hours for 6 and then of 0.2°C every 2 hours for 6 hours to the goal temperature of 36.5°C (see Appendix 1 for temperature management worksheet phase 1). The intensity and frequency of post-operative monitoring will be exactly the same in the experimental group as in standard of care group, including post-operative EEG, serum biomarker testing and neurodevelopmental follow up. The following parameters will be observed in the experimental group and compared with the standard of care group.

1. Hemodynamic status-Infants who are hypothermic typically have lower resting heart rates than those who are normothermic (80-100 beats per minute versus 120-140 beats per minute respectively). In the post-operative congenital heart infant, bradycardia (slow heart rate) could conceivably have an adverse impact on the hemodynamic status of the infant and if untreated this could also impact renal function. Hemodynamic status will be continuously monitored in the same manner as detailed in the standard of care section. Intravenous medications to support cardiac function and blood pressure (which these infants are typically already treated with) will be up-titrated if necessary. The need for permanent pacemaker implantation will be documented.

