Human Subjects Involvement, Characteristics and Design: The goal of this research is improve developmental outcomes in infants who have undergone congenital heart surgery. Infants who require surgical correction of congenital heart defects are often treated with hypothermia during the surgery to protect the brain. Following completion of congenital heart surgery, the current standard of care is to rapidly rewarm them on cardiopulmonary bypass to normothermia. This rapid rewarming is thought to have adverse effects on the brain. This project proposes to partially rewarm infants to 35°C on bypass and then complete rewarming over the first 12 hours after surgery in the intensive care unit using an FDA approved machine that can carefully control body temperature changes by small increments. In this project, safety of the

“delayed rewarming” technique will be assessed and we will ultimately aim to assess efficacy in a larger future trial if safety can be shown first.

The study of human subjects is therefore necessary to achieve the goals presented in this application. The proposed clinical research for specific aims 1 and 2 will involve human subjects prospectively recruited from Maine Medical Center located in Portland, Maine. As the only pediatric tertiary care center in the state, the catchment area is large. Included subjects will be less than 12 months of age. Each subject must undergo congenital heart surgery with cardiopulmonary bypass before the age of 12 months. We aim to recruit 30 infants over a 24 month period. It is expected that there will be an equal proportion of male and female subjects. It is expected that the racial and ethnic composition of subjects will reflect the racial homogeneity of the state of Maine.

Infants will be randomized to one of two groups; the standard of care group versus the experimental group. Infants in the experimental group will receive the delayed rewarming therapy, which consists of stopping rewarming on bypass at either 35 °C and gradual rewarming over 12 hours to normothermia through use of a servo-controlled temperature regulating blanket. Adverse events such as effects on hemodynamic status, coagulation status, rate of infection and incidence of subcutaneous fat necrosis will be compared between groups as will serum biomarkers of neuronal injury.

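### Neither Bayley timing rule sets a minimum interval after surgery, and no analysis accounts for it, so a between-arm trend in Bayley scores would be hard to read

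*Combined protocol and SAP*

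**What the plan says.** The protocol states the timing of the Bayley assessment twice.

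- Specific Aim 2.3: "Bayley testing will be performed on infants at either 6 or 12 months of age depending on the" (the sentence ends by naming age at surgery as the deciding factor). It does not say which ages at surgery lead to the 6-month test and which to the 12-month test.
- Materials and Methods, Standard of care group, third deviation from routine care: "Bayley Infant Scales of Development (Bayley 3) will be performed between age 9 months and 2 years".

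The Experimental group section applies the same schedule to the other arm, "including post-operative EEG, serum biomarker testing and neurodevelopmental follow up", so the test is meant to follow surgery.

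Age at surgery is limited only from above: "Each subject must undergo congenital heart surgery with cardiopulmonary bypass before the age of 12 months" (Human Subjects Involvement, Characteristics and Design). The one description of age at surgery comes from the 15 survivors reviewed to set the adverse-event limits in Table 1: "the mean age at the time of surgery was 148 days with a range from 4 to 356" days.

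Developmental outcome is a secondary outcome (Anticipated outcomes). The Analysis section lists age in months among the baseline variables. It specifies tests for adverse events and for the serum biomarkers, but none for the Bayley scores.

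**The concern.** A developmental score is useful here if it reflects how the infant has developed since the intervention. Both rules are expressed in the infant's age, and surgery can happen at any point in the first year. The time between bypass and test is therefore whatever remains after subtracting one age from the other. A score taken days after bypass may largely reflect hospital stay and recovery, while a score taken a year or more later may not.

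Aim 2.3 hopes to see a trend towards better scores with delayed rewarming. If time since surgery varies widely and is neither controlled nor adjusted for, a trend in either direction could come from a difference between the arms in age at surgery. A badly timed assessment cannot be repaired after the data are in.

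Choosing between the two rules does not settle this. The only age that satisfies both is 12 months, and that is the test with the 9-day gap.

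**Working it through.** The documents give no surgery-to-test interval, so there is no stated figure to reproduce. The check is subtraction.

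**Inputs.** Ages at surgery of 4, 148 (mean) and 356 days, from the retrospective series described before Table 1. Test ages of 6 and 12 months (Aim 2.3) and 9 to 24 months (standard-of-care section). With a 365-day year, 6, 9, 12, 18 and 24 months are 182.5, about 274, 365, 547.5 and 730 days. The 18-month age is not in the protocol; it is included to examine a possible fix.

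**Formula.** Gap = age at test − age at surgery.

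| Age at surgery | Test at 6 mo | 9 mo | 12 mo | 18 mo | 24 mo |
|---|---|---|---|---|---|
| 4 days | 178.5 | 270 | 361 | 543.5 | 726 |
| 148 days | 34.5 | 126 | 217 | 399.5 | 582 |
| 356 days | not possible after surgery | −82 | 9 | 191.5 | 374 |

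**Aim 2.3 alone.** For any infant operated on after 6 months, 12 months is the only post-operative option, so surgery at day 356 gives 365 − 356 = 9 days. The longest gap is 365 − 4 = 361 days. If each infant is tested at the next milestone (an assumption, since no cut-off is given), short gaps also occur in the first half-year: surgery at day 170 gives 182.5 − 170 = 12.5 days. The clause linking test age to age at surgery therefore sets no floor.

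**Standard-of-care section alone.** The longest gap is 730 − 4 = 726 days. Read literally, the window opens before surgery for any infant operated on after about day 274; at day 356 it opens 356 − 274 = 82 days before.

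**How short is 9 days?** Table 1 counts intubation as an event only beyond 5 days, and use of more than two pressors only beyond 7 days. An infant tested on day 9 could have come off such support 9 − 7 = 2 days earlier without crossing either limit. The documents give no recovery time as such.

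**Chance imbalance.** As an illustration only, suppose age at surgery is uniform over 4 to 356 days. The SD is 352/√12 ≈ 102 days. The standard error of the difference in mean age between arms of 15 is 102 × √(2/15) ≈ 37 days, a 95% range of about ±73 days. At a fixed test age, that becomes an equal difference in mean time since surgery.

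**Effect of a later test age.** At 18 to 24 months, the gap runs from 547.5 − 356 = 191.5 days to 730 − 4 = 726 days. The eligibility limit guarantees 18 − 12 = 6 months. The spread does not shrink: it is 726 − 191.5 = 534.5 days, against 361 − 9 = 352 days for a single test at 12 months. A later age raises the floor but does not remove an imbalance.

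**The case against.** Several points on the other side stand.

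- **The two schedules must not be merged.** A reader might infer one range, from 9 days or even before surgery up to nearly 2 years. No single rule gives it: 9 and 361 days belong to Aim 2.3, and the pre-surgical opening and 726 days belong to the standard-of-care section.
- **Testing before surgery is not intended.** It follows only from a literal reading of a window, and the Experimental group section calls the assessment follow-up. The −82 days shows loose wording, not a plan.
- **Aim 2.3 does take surgery into account.** Its choice of test age depends on age at surgery, presumably to keep the test post-operative. It still states neither a cut-off nor a minimum gap.
- **The arms are treated alike.** The same rule applies to both, so 1:1 randomisation balances the gap in expectation. The Analysis section also concedes that randomisation may not balance so small a sample, and promises to look for biases when interpreting the findings. That is a caution, not an adjustment.
- **The extremes may be rare.** They come from 15 retrospective survivors. At their mean age of 148 days, a 12-month test falls 217 days after surgery. The share of trial infants who would be tested within weeks of bypass is unknown.
- **Bayley is not the gateway to the next trial.** The protocol makes safety the condition for an efficacy study and claims no power.

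Design Figures 3a and 3b are not reproduced in the text available, so timing shown there cannot be ruled out.

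**Conclusion.** The point holds as a weakness in how a secondary outcome is measured. Neither written rule sets a minimum post-surgical interval, and Aim 2.3 followed as written puts the test about 9 days after bypass for an infant operated on at day 356. Gaps can reach about 361 days under Aim 2.3 and about 726 days under the other rule. No planned analysis takes this into account.

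A reader might go further and infer that the Bayley comparison is biased, or that the case for a later trial is undermined. The documents support neither. The consequence is added variability and possible chance imbalance with 15 per arm, which make a trend hard to interpret in either direction.

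The gaps rest on the retrospective age range carrying over to the trial; the protocol says of that series "These infants had a mix of cardiac lesions similar to those who would be enrolled in this study". The ±73 days rests on the uniform-age assumption. That very early scores reflect recovery is a reasonable inference, but the documents do not quantify it. The change should be made before testing begins.

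**What to change.** When the two timing statements are reconciled:

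1. Give one rule for all infants, inside the window up to 2 years that the protocol already permits, with a common test-age window and a stated minimum interval after surgery. Testing at 18 to 24 months of age is one example and guarantees about 6 months. A narrower window would reduce the spread, and another age would serve if the minimum is stated.
2. Record the surgery-to-test interval for each infant and report it by arm.
3. Add a Bayley analysis to the Analysis section that adjusts the between-arm comparison for age at surgery. This is a baseline variable already collected, and it is needed because a fixed test age passes an imbalance in age at surgery straight into recovery time.
4. If an earlier test is kept for referral, report it separately and leave it out of the between-arm comparison.

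The cost is protocol wording, one derived variable and a short analysis statement. Results could come up to 12 months later than the Aim 2.3 limit (24 − 12 months), though no later than the other rule already allows, and loss to follow-up may rise. Potential Benefits of the Proposed Research counts early assessment and earlier referral as a benefit to participants. Later testing gives up some of that, and keeping an early test to preserve it means an additional assessment.
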